15.2 DECIT (2–deoxy–5–azacytidine), Decitabine, Dacogen®

15.21 Background: Decitabine is directly incorporated into DNA and causes inhibition of DNA methyltransferase, leading to hypomethylation of DNA and cellular differentiation or apoptosis. Decitabine-induced hypomethylation in neoplastic cells may restore normal function to genes that are critical for the control of cellular differentiation and proliferation.

15.22 Formulation: Decitabine for injection is a white to almost white sterile lyophilized powder supplied in a clear colorless glass vial. Each 20 mL, single dose, glass vial contains 50 mg decitabine, 68 mg monobasic potassium phosphate (potassium dihydrogen phosphate) and 11.6 mg sodium hydroxide.

15.23 Preparation and Storage: Decitabine should be aseptically reconstituted with 10 mL of Sterile Water for Injection (WFI); upon reconstitution, each mL contains approximately 5 mg of decitabine at pH 6.7-7.3. Immediately after reconstitution, the solution should be further diluted per recommended procedure with infusion fluids, such as 0.9% Sodium Chloride Injection or 5% Dextrose Injection to a final drug concentration of 0.1 - 1.0 mg/mL. Unless used within 15 minutes upon reconstitution, the diluted solution must be prepared using cold infusion fluids and stored at 2-8°C for a maximum of 4 hours prior to administration. Each 20-mL vial contains 50 mg decitabine.

15.24 Administration: Decitabine is administered intravenously over 1 hour.

15.25 Pharmacokinetic information

Distribution: Approximately 63 to 89 L/m²

Metabolism: Possibly via deamination by cytidine deaminase

Half-life elimination: Approximately 30 to 35 minutes

15.26 Known potential drug interactions: No known cytochrome P450 drug-drug interactions. Concomitant use with known myelosuppressive agents may enhance the adverse/toxic effects.

15.27 Known potential toxicities:

Common known potential toxicities, > 10%:

Cardiovascular: Peripheral edema, pallor, edema, cardiac murmur, hypotension

Central nervous system: Fever, fatigue, headache, insomnia, dizziness, chills, pain, confusion, lethargy, anxiety, hypoesthesia

Dermatologic: Petechiae, bruising, rash, erythema, cellulitis, lesions, pruritis

Endocrine & metabolic: Hyperglycemia, hypoalbuminemia, hypomagnesemia,

hypokalemia, hyperkalemia, hyponatremia

Gastrointestinal: Nausea, constipation, diarrhea, vomiting, anorexia, abdominal pain, stomatitis, dyspepsia

Hematologic: Neutropenia, thrombocytopenia, anemia, febrile neutropenia, leukopenia, lymphadenopathy

Hepatic: Hyperbilirubinemia, alkaline phosphatase increased

Neuromuscular & skeletal: Rigors, arthralgias, limb pain, back pain, weakness

Respiratory: Cough, dyspnea, pneumonia, pharyngitis, lung crackles, heart failure

Less common known potential toxicities, 1% - 10%:

Cardiovascular: Tachycardia, chest pain/discomfort, facial edema, hypertension, heart failure

Central nervous system: depression, malaise

Dermatologic: Alopecia, dry skin, urticarial

Endocrine & metabolic: Hyperuricemia, LDH increased, bicarbonate increased or decreased, dehydration, hypochloremia, hypoproteinemia

Gastrointestinal: Mucosal inflammation, weight loss, gingival bleeding, hemorrhoids, loose stools, tongue ulceration, dysphagia, oral candidiasis, toothache, abdominal distension, gastroesophageal reflux (GERD), glossodynia, lip ulceration, oral pain, tooth abscess

Genitourinary, urinary tract infection, dysuria, polyuria

Hematologic: Bacteremia, hematoma, pancytopenia, thrombocythemia

Hepatic: Ascities, AST increased, hypobilirubinemia

Neuromuscular & skeletal: Myalgias, falling, chest wall pain, muscle spasms, bone pain, musculoskeletal discomfort

Ocular: Blurred vision

Otic: Ear pain

Respiratory: Abnormal breath sounds, hypoxia, upper respiratory tract infections, pharyngolaryngeal pain, rales, pulmonary edema, sinusitis, pleural effusion, postnasal drip, sinus congestions

Miscellaneous: Candidal infections, staphylococcal infection, transfusion reaction, night sweats

Rare known potential toxicities, <1% (Limited to important or life-threatening):

Anaphylactic reaction, atrial fibrillation, bronchopulmonary aspergillosis, cardiomyopathy, cardiorespiratory arrest/failure, catheter site hemorrhage, cholecystitis, fungal infection, gastrointestinal hemorrhage, gingival pain, hemoptysis, hypersensitivity, intracranial hemorrhage, mental status change, MI, mycobacterium avium complex infection, peridiverticular abscess, pseudomonal lung infection, pulmonary embolism, pulmonary infiltrates, pulmonary mass, renal failure, respiratory arrest, sepsis, splenomegaly, supraventricular tachycardia, Sweet's syndrome (acute febrile neutrophilic dermatosis), urethral hemorrhage

15.28 Drug procurement: Commercial supplies. Pharmacies or clinics shall obtain supplies from normal commercial supply chain or wholesaler. 15.2 DECIT (2-deoxy-5-azacytidine), Decitabine, Dacogen®

15.29 Nursing Guidelines:

- 1) Monitor CBC. Myelosuppression is a dose limiting factor. Instruct patient to report any signs or symptoms of infection, unusual bruising or bleeding to the health care team.
- 2) Nausea and vomiting is common. Premedicate with antiemetics and assess for their effectiveness.
- 3) Certain infections were seen more commonly in patients treated with decitabine; including pneumonia, fungal, candidal, infections and cellulitis. Instruct patient to report any signs or

symptoms of infections immediately.

- 4) Patients may experience fatigue. Instruct in an energy conserving lifestyle.
- 5) Monitor liver function tests. Report any abnormalities to the treating MD.
- 6) Please note that not all nursing guidelines may be known at this time. Monitor patient carefully and report all adverse events to the MD and as required by your institution for adverse event monitoring.

16.0 Statistical Considerations and Methodology

16.1 Overview: This is a phase II study of a combination of midostaurin and decitabine in elderly patients with newly diagnosed AML and FLT3 mutation. This study will use a one-stage binomial design to assess the efficacy of this combination.

16.11 Endpoint: The primary endpoint in this trial is the proportion of complete responses during therapy. A success is defined as a CR or CRi as the objective status during therapy. Throughout Section 16.0, complete response will be considered synonymous with “success”, unless specified otherwise. All patients meeting the eligibility criteria who have signed a consent form and have begun treatment will be evaluable for response.

16.2 Statistical Design:

16.21 Decision Rule:

In previous studies of elderly AML patients treated with single agent decitabine as frontline therapy, complete response rates of 15%-24% were seen (Cashen, 2010 #813} {Lubbert, 2007 #812}). An improvement in complete response rate with the addition of midostaurin to decitabine would be of interest.

The largest success proportion where the proposed treatment regimen would be considered ineffective in this population is 10%, and the smallest success proportion that would warrant subsequent studies with the proposed regimen in this patient population is 30%. A one-stage binomial design uses 24 evaluable patients to test the null hypothesis that the true complete response rate is at most 10%.

16.211 Final Decision Rule: Enter 24 evaluable patients into the study. If 4 or fewer successes are observed in the first 24 evaluable patients, we will consider this regimen ineffective in this patient population. If 5 or more successes are observed in the first 24 evaluable patients, we may recommend further testing of this regimen in subsequent studies in this population.

- 16.212 Over Accrual: If more than the target number of patients are accrued, the additional patients will not be used to evaluate the stopping rule or used in any decision making process. Analyses involving over accrued patients are discussed in Section 16.34.
- 16.22 Sample Size: This study is expected to require 24 evaluable patients. We anticipate accruing 2 additional patients to account for ineligibility, cancellation, major treatment violation, or other reasons. Therefore, the study is expected to accrue a maximum of 26 patients overall.
- 16.23 Accrual Rate and Study Duration: The anticipated accrual rate is 1 evaluable patient per month. Therefore, the accrual period is expected to be approximately 2 years. The primary endpoint will be evaluated approximately 2.75 years after the trial opens, or after the last patient accrued has been observed for at least 6 months. The total study duration is expected to be approximately 3 years.
- 16.24 Power and Significance Level: Assuming that the number of successes is binomially distributed, the significance level is .09, i.e. there is a 9% chance of finding the drug to be effective when it truly is not. The probability of declaring that this regimen warrants further study (i.e. statistical power) under various success proportions can be tabulated as a function of the true success proportion as shown in the following table.

If the true success proportion is...	0.10	0.15	0.20	0.25	0.30
Then the probability of declaring that the regimen warrants further study is...	0.09	0.29	0.54	0.75	0.89

- 16.25 Other considerations: Adverse events, quality/duration of response, and patterns of treatment failure observed in this study, as well as scientific discoveries or changes in standard care will be taken into account in any decision to terminate the study

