The presence of FLT3-ITDs has been found in certain studies to be the strongest predictor of patient outcome ([Kottaridis 2001](#), [Kiyoi 1999](#)). AML patients harboring FLT3 ITD mutations are characterized by certain pretreatment features like higher levels of white blood cell counts and blood and bone marrow blasts ([Frohling 2002](#), [Thiede 2002](#)). FLT3 ITD has been reported consistently as an unfavorable prognostic marker for relapse-free (RFS) and overall survival (OS) ([Kottaridis 2001](#), [Frohling 2002](#), [Thiede 2002](#), [Gale 2008](#)). In a study of 854 AML patients, an ITD was present in 27% of the patients. Although presence of FLT3 mutation did not impact CR rate, long term clinical outcomes varied based on the presence of FLT3 ITD. The relapse rate at 5 years was 64% in patients with the mutation versus 44% in those without. Disease free survival at 5 years was 30% compared to 46% in patients without a mutation and overall survival of 32% compared to 44% of patients without the mutation. ([Kottaridis 2001](#))

Furthermore, additional factors of the FLT3 ITD mutation may impact outcome, including size of the base pair insertion, higher allelic ratio (mutant: wild-type FLT3) and insertion site ([Stirewalt 2006](#), [Thiede 2002](#), [Kayser 2009](#)) As details of FLT3 ITD mutations continue to be evaluated, it remains clear that AML with a FLT3 ITD mutation results in higher relapse, shorter DFS and shorter OS which has led to an increased focus on HSCT in CR1 in this group.

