Overall, AEs suspected to be related to midostaurin treatment were mostly Grade 1 and 2 gastrointestinal events requiring little or no intervention. These were considered related to midostaurin, as the frequency increased at higher dose levels. At the 100 mg twice daily dose in AML patients with chemotherapy, patients discontinued treatment more frequently due to nausea and vomiting despite addition of antiemetic therapy which contributed to selection of a 50 mg twice daily dose which was found to be well tolerated. In addition to prophylactic anti-emetics, administering the doses with meals can reduce gastrointestinal AEs. These AEs are most common in the early cycles of administration. In the ongoing ASM/MCL studies, patients are tolerating the 100 mg twice daily dose for up to 4 years; however, prophylactic anti-emetics are given to all patients.

Overview of decitabine

Decitabine, one of the hypomethylating agents, is FDA approved for the management of myelodysplastic syndrome. In Europe decitabine is also approved for AML in elderly patients 65 or older. It has been also found to be effective in patients with AML. For elderly AML patients unfit for chemotherapy, hypomethylating agents are the cornerstone for treatment due to its low toxicity and safe profile. In a phase III study (Kantarjian 2012), decitabine given 20 mg/m² as 1-hour intravenous infusion daily for five days every four weeks improved response rates compared with standard therapies without major differences in safety. CR was achieved in 18% with decitabine versus 8% in the other arm.

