2.0 Goals

2.1 Primary

2.11 To determine the complete response rate for elderly patients with FLT3 mutated AML using midostaurin and decitabine

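### The 9% error in 16.24 holds for CR/CRi rates up to 10%; it is not the chance of a pass when midostaurin adds nothing to decitabine, which is 0.29 to 0.72 if the cited decitabine rates carry over

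*Combined protocol and SAP*

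**What the plan says.** Section 16.21 starts from earlier studies of elderly AML patients "treated with single agent decitabine as frontline therapy, complete response rates of 15%-24% were seen". It then gives the motivation for the trial: "An improvement in complete response rate with the addition of midostaurin to decitabine would be of interest". The null follows: "The largest success proportion where the proposed treatment regimen would be considered ineffective in this population is 10" percent. The rate that would warrant further study is 30%. No reason is given for choosing 10%.

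Section 16.211 gives the rule: "If 5 or more successes are observed in the first 24 evaluable patients, we may recommend further testing of this regimen". A success is a CR or a CRi (16.11).

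Section 16.24 states a significance level of .09 and explains it in words: "there is a 9% chance of finding the drug to be effective when it truly is not". Its table gives the probability of a pass as 0.09, 0.29, 0.54, 0.75 and 0.89 at true rates of 10%, 15%, 20%, 25% and 30%.

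Two other places bear on the benchmark. Section 1.2, on a phase III study, reports: "CR was achieved in 18% with decitabine versus 8% in the other arm". Section 2.11 states the primary goal: "To determine the complete response rate for elderly patients with FLT3 mutated AML using midostaurin and decitabine".

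**The concern.** The null lies below every decitabine-alone rate the protocol cites. The 8% in 1.2 belongs to the comparator arm, so it is not an exception. On those figures, a combination in which midostaurin contributes nothing would not fall under the null at all. The 9% would then not be the chance that it passes.

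The gloss in 16.24 speaks of the drug being found effective when it is not. Coming after 16.21's interest in what midostaurin adds, it invites the reader to take 9% as the chance of wrongly crediting midostaurin. The table covers the relevant span, but nothing tells the reader that 15% to 25% contains the rates cited for decitabine alone. Section 16.211 does not say what a pass does and does not establish.

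What is at stake is the reading of a positive result. The smallest pass, 5/24 = 20.8%, lies inside the cited 15%-24%. A follow-on study could be justified by a result that decitabine alone would often produce.

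**Working it through.** **Inputs.** n = 24 and a pass at 5 or more (16.211); null rate 10% and target rate 30% (16.21); decitabine-alone rates 15%-24% (16.21) and 18% (1.2). One further rate, 12%, is an assumption. It stands for a population that does worse than the cited studies.

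**Formula.** With X the number of successes, P(X ≥ 5) = 1 − Σ C(24,k) p^k (1−p)^(24−k), summed over k = 0 to 4.

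**The plan's own figures first.** At p = 0.10 the five terms are 0.0798, 0.2127, 0.2718, 0.2215 and 0.1292. They sum to 0.9150 (0.9149 before the terms are rounded), so the tail is 0.0851, printed as .09. At 15%, 20%, 25% and 30% the tails are 0.2866, 0.5401, 0.7534 and 0.8889. All five table entries reproduce. At 8% the tail is 0.0386. The tail rises with p, so 0.085 is the maximum over all rates up to 10%.

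**Chance of a pass if midostaurin adds nothing**

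| Assumed decitabine-alone CR/CRi rate | P(5 or more of 24) |
|---|---|
| 12% (assumed) | 0.153 |
| 15% (16.21, low end) | 0.287 |
| 18% (1.2) | 0.439 |
| 24% (16.21, high end) | 0.717 |

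**What the smallest passes can reject.** One-sided exact p-values:

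| Successes | against 10% | against 15% |
|---|---|---|
| 5 | 0.085 | 0.287 |
| 6 | 0.028 | 0.139 |

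At the trial's one-sided 9% level, 5 or 6 successes rejects 10% but not 15%, and so none of the higher cited rates either. The smallest counts that reject the cited rates at that level are 7 for 15% (p = 0.057), 8 for 18% (0.053) and 10 for 24% (0.042). These counts treat the historical rates as known constants. They are shown for scale and are not proposed as cut-offs.

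**How often a pass is that small.** At a true rate of 30%, P(X = 5 or 6) = P(X ≥ 5) − P(X ≥ 7) = 0.8889 − 0.6114 = 0.2775, or about 28% of trials.

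**Interval at the smallest passes.** The exact two-sided 95% interval is 7.1%-42.2% for 5/24 and 9.8%-46.7% for 6/24. Both contain 10%. Any statement that 5 successes rejects 10% must therefore name the one-sided 9% level, or it will appear to contradict the interval printed beside it.

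**The case against.** The plan does not claim superiority over decitabine. Its primary goal is to determine the CR rate, its null concerns the regimen's own rate, and 16.211 says only that further testing may be recommended. The sentence about improvement is motivation, not a tested hypothesis. The choice of null in a single-arm phase II trial is a design judgement. The 16.24 table already prints 0.29, 0.54 and 0.75 at 15%, 20% and 25%, and 16.312 already plans an estimate with exact intervals.

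Carry-over is also not established. The documents give no decitabine-alone rate for FLT3-mutated patients. Section 1.1 reports of 854 AML patients: "Although presence of FLT3 mutation did not impact CR rate". That leans toward carry-over, but the title of that reference describes chemotherapy. This trial takes patients who are unfit for intensive induction or decline it, with performance status up to 3 (3.12, 3.14), and allows secondary AML (3.27). Their rate could be lower. In the other direction, the documents do not say whether the cited rates include CRi. If they do not, the decitabine-alone CR/CRi rate would be no lower than cited, and nor would the chance of a pass.

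Most of this stands. It rules out two stronger readings that a reader might infer. The first is that 9% is miscalculated; it reproduces exactly for the null as written. The second is that the trial's true type I error is 29%-72%, so that the null must be raised. That would require both a superiority claim the plan does not make and a carry-over it does not show.

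What the objection does not remove is the gap in the text. The table is not linked to decitabine, no reason is given for 10%, 16.312 names no confidence level, and the gloss in 16.24 is broader than the null it describes.

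**Conclusion.** The point holds as a matter of what the stated error means and what a pass can support. For true CR/CRi rates of 10% or lower, 9% is right. For improvement over decitabine alone, the chance of a pass with no midostaurin effect is 0.29 to 0.72 if the cited 15%-24% applies here, and 0.15 at an assumed 12%. All of these exceed 9%.

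A pass at 5 or 6 successes supports a rate above 10% at the one-sided 9% level, which fits goal 2.11. It does not support the improvement named in 16.21. The size depends on the carry-over assumption and on whether the cited rates count CRi, and the documents settle neither. The arithmetic is certain. The point should be fixed because the present wording invites a materially wrong reading of a positive trial.

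**What to change.** Two wording changes, with the null, cut-off, n and power unchanged.

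1. In 16.24, replace the sentence that explains the 9% with: *The one-sided significance level is at most 9% for true CR/CRi rates of 10% or lower. If the true rate equals the cited decitabine-alone rates of 15%-24%, the probability of 5 or more successes is 29%-72%.*

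2. In 16.211, add as a descriptive statement and not as a further criterion: *Five or more successes rejects a rate of 10% or lower at the one-sided 9% level and does not by itself show improvement over decitabine alone; the estimate and its exact two-sided 95% confidence interval (which includes 10% at 5 or 6 successes) will be reported alongside the cited 15%-24%.*

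**Cost.** The text is trivial to add. The 5-of-24 rule and the power of 0.89 at 30% are untouched, because the added sentence gates nothing. The real cost is a less favourable stated error and a narrower claim from a positive result. A different null, cut-off or sample size would be a trade-off for the sponsor and is not part of this change.
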